CLINICAL INVESTIGATION PLAN

Prospective, multi - centre clinical evaluation of the performance and safety of the HYPERION hip endoprosthesis system in defect reconstruction

Protocol version: Rev.03; 4th June 2015

Protocol Number: BMETEU.CR.EU79.10

NCT Number: NCT03382665

STUDY SPONSOR

Zimmer GmbH
[name]
P.O. Box
[name]
Switzerland

Study Summary

Title:	Prospective, multi - centre clinical evaluation of the performance and safety of the HYPERION hip endoprosthesis system in defect reconstruction
Sponsor:	Zimmer GmbH
Objectives/ Endpoints	
The data collected from this post-market clinical follow up study will serve the purpose of confirming long-term safety and performance of the Hyperion system. To this aim, the Hyperion system will be evaluated using standard scoring systems, radiographs and the reporting of adverse events. Patients having received the Hyperion hip replacement stem will be followed up after 1 week, 3 month, 6 month, 1, 2 and 5 years assessing clinical and radiographic outcomes. In addition, after 7- and 10- years the patients will be asked to fill in a questionnaire recording the patients mid-to long-term clinical satisfaction.
 
Primary endpoints:
 
1. Merle d'Aubigné score 
Endpoint: Merle d' Aubigné Score increase of min. 4 points at 2 years post surgery, compared to the pre-operative score points (< 12 points).
 
2. Implant survival at 2 years (+/- 2 months)3. Western Ontario and McMaster Universities Osteoarthritis Index (WOMAC) scores 
Endpoint: Decrease in min. 25 points in the WOMAC Score compared to the pre-operative determined points (WOMAC Score > 25 points pre-operative). The primary outcome measure is at 2 years (+/- 2 month).

Indication/ Target Population:	Patients, suffering from severe hip pain and disability requiring total hip arthroplasty, who meet the inclusion/exclusion criteria
Study Design:	Multi-center, prospective, non-controlled
Clinical Phase:	Post-market
Number of Subjects:	A total of 70 patients will be enrolled

Length of Study:	12 years
Study Device:	Hyperion System
Clinical Assessments	Merle d`Aubigné Score, WOMAC scores and radiographic assessments.
Safety Assessments:	Safety will be assessed by appropriate recording and reporting of adverse events throughout the study. All system components are CE marked and commercially available.
Statistical Analysis	Data collected will be summarized and reported to each participating Investigator. Statistical analysis is conducted by Zimmer or its designee.

General Statistical Method:

Data collected in the study will be summarized descriptively. Descriptive summaries will be used for the basis of all study reports, including a summary of the clinical performance of the HYPERION hip endoprosthesis system in defect reconstruction, and may be used for reports and to support presentations and publications as needed.

Summaries will routinely describe categorical data as counts and percentages, and ninety-five percent confidence limits will be generally used to assess differences over time. Routine summaries describing continuous data will be in the form of means, medians, standard deviations, minima, and maxima, and ninety five percent confidence intervals will be used to contrast differences.

Routine summaries of implant survival will be described using the Kaplan-Meier method.

Routine summaries of complication data will be in the form of frequencies and percentages.

Summaries may be further generated for strata within the study population, such as males/females, body mass index or primary diagnosis.

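### Does a 25-point WOMAC fall from a baseline only just above 25 shut out patients who improve greatly, so that mean change should lead?

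*Combined protocol and SAP*

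**What the plan says.** Under Objectives/Endpoints, the Study Summary sets the WOMAC endpoint as "Decrease in min. 25 points in the WOMAC Score compared to the pre-operative determined points (WOMAC Score > 25 points pre-operative", and adds "The primary outcome measure is at 2 years (+/- 2 month". It does not name the WOMAC version or its range. It does not say whether the 25 points apply to each patient or to the group mean, and it gives no proportion of patients who must reach them.

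The design is "Multi-center, prospective, non-controlled", and the sample size is given as "A total of 70 patients will be enrolled". The target population is "Patients, suffering from severe hip pain and disability requiring total hip arthroplasty".

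The General Statistical Method is descriptive throughout. Categorical data get counts and percentages with 95% limits. For continuous data, "Routine summaries describing continuous data will be in the form of means, medians, standard deviations, minima, and maxima, and ninety five percent confidence intervals" are planned. On subgroups it says: "Summaries may be further generated for strata within the study population, such as males/females, body mass index or primary diagnosis". It does not say which WOMAC summary leads, and pre-operative score is not among the named examples.

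**The concern.** The required fall (25) is the same number as the baseline condition, "WOMAC Score > 25 points pre-operative". A patient just above the cut-off must therefore lose almost the whole score to count as a success, while a patient with a high score needs only a modest relative gain. Going from 30 to 6, an 80% fall, fails; going from 30 to 5 succeeds; going from 75 to 50, a 33% fall, also succeeds.

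Two things would be at stake. The reported success rate would depend partly on how many patients start near 25, and in a study without a comparison arm a low rate in that group could be mistaken for poor implant performance. Dichotomising the score also discards information. The natural suggestion is to make mean within-patient change the lead WOMAC result and to move the 25-point rate to second place.

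**Working it through.** **Inputs from the plan.** Required fall 25; baseline above 25; 70 patients; one group; descriptive analysis. The plan gives no power, target proportion or SD, so there is no calculation of the 70 to reproduce.

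**Step 1: what the rule demands.** Assume a per-patient reading and a minimum score of 0. The highest passing 2-year score is baseline − 25, and the required relative fall is 25 / baseline.

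| Baseline | Highest passing score | Required fall |
|---|---|---|
| 26 | 1 | 25/26 = 96% |
| 30 | 5 | 25/30 = 83% |
| 35 | 10 | 25/35 = 71% |
| 50 | 25 | 25/50 = 50% |
| 75 | 50 | 25/75 = 33% |

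A patient who improves by a fraction r misses only if baseline < 25/r: below 31.25 for r = 0.8 and below 35.7 for r = 0.7. Great improvement with a miss is therefore confined to a narrow band above 25.

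**Step 2: how many patients that is.** The plan gives no baseline distribution, so this step rests on assumptions: a 0–100 scale, baseline SD 18 (kept if above 25), 2-year SD 15 limited to 0–100, correlation 0.3, baseline mean 45, 55 or 60, and 2-year mean 15, 20 or 25. Simulating the nine combinations gives:

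| Patients who miss despite a fall of at least | Base case (55/20) | Nine scenarios | Most, of 70 |
|---|---|---|---|
| 80% | 0.2% | 0.1–0.6% | 0.006 × 70 = 0.4 |
| 70% | 0.8% | 0.4–1.8% | 0.018 × 70 = 1.3 |
| 50% | 4.8% | 3–8% | 0.08 × 70 = 5.6 |

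A second assumed model (baseline mean 40 to 60, SD 12 to 18; percentage improvement averaging 60% or 75%, SD 20 points) gives 0.2–6.2% at the 70% level, or about 0 to 4 of 70. At the 50% level it gives 2.3–23.9%, or about 2 to 17 of 70. The higher values arise when the baseline mean is as low as 40.

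The larger counts therefore come from the 50% definition, which is not in the plan. Halving a score of 40 is a 20-point fall, and leaving it below a 25-point bar is what a fixed bar is meant to do.

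**Step 3: whether mean change cures the dependence on baseline.** First model, one mean moved at a time:

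| Summary | Baseline mean 45 → 60 (2-year mean 20) | 2-year mean 15 → 25 (baseline mean 55) | Ratio |
|---|---|---|---|
| 25-point rate | 57% → 79%: 22 percentage points | 81% → 63%: 18 percentage points | 22/18 = 1.2 |
| Mean change | 27.8 → 40.2: about 12.3 points | 40.2 → 31.1: 9.1 points | 12.3/9.1 = 1.4 |

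On this comparison mean change is no less sensitive to baseline mix than the rate. The reason is simple: nobody can fall by more than the starting score. In the base case, mean change is about 15 points for baselines of 25–35 and 48 points above 60.

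**Step 4: precision.** In the base case at n = 70, the rate has a 95% half-width of 1.96 × √(0.724 × 0.276 / 70) = 10.5 percentage points. Mean change has 1.96 × 18.2 / √70 = 4.3 points. Both intervals are already among the planned summaries.

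**The case for a change.** The strongest case for a change is this. The cliff is real on the natural per-patient reading, which is supported by the pairing of the threshold with a baseline condition and by the similar form of the Merle d'Aubigné endpoint. In the base case, 9% of patients (about 6 of 70) start at 25–35, and only 28% of them succeed, against 93% of those above 60. Mean change has no cliff. At 72% success a proportion carries about 56% of the information in a mean for normal data. The change would cost only wording.

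Much of this stands as description: the gradient by baseline is real, and a mean is the more efficient summary. It does not carry the recommendation. Mean change has its own steep gradient by baseline, so only a table by pre-operative score would show the dependence, and producing one does not require demoting the endpoint. The efficiency loss would matter if a test or a sample size rested on the rate, and neither does. A mean also does not show how many patients benefited, which the rate does. If the 25 points were meant for the group mean, no individual failures arise and mean change is already the endpoint.

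**Conclusion.** No change is needed. The arithmetic behind the concern is correct on a per-patient reading with a minimum of 0, but the patients it describes, those who improve greatly and still miss, number about 1 of 70 at most under the first set of assumptions and up to about 4 of 70 under the second. The plan gives no baseline distribution, so these counts are illustrations rather than estimates. A population with severe pain and disability may have few patients near 25. The baseline condition also has a sensible purpose: it makes a 25-point fall attainable for everyone counted.

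Choosing a responder rate over a mean is a fair trade-off between a result that is easy to communicate and one that uses the data more fully. Both will be reported anyway, with intervals, in a study that sets no success proportion, so re-ranking them would alter no result or conclusion. The unstated WOMAC version, the score range and the per-patient or group reading are gaps that competent analysts fill when reporting. A breakdown by pre-operative score fits within the plan's open list of strata and would help readers interpret the rate, but the planned results are sound without it.

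### Must the plan fix the denominator and a revision rule for the two 2-year score endpoints?

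*Combined protocol and SAP*

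**What the plan says.** The Study Summary, under Objectives/Endpoints, lists three primary endpoints.

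- **Merle d'Aubigné:** "increase of min. 4 points at 2 years post surgery, compared to the pre-operative score points (< 12 points").
- **Implant survival:** at 2 years, with a window of 2 months either way.
- **WOMAC:** "Decrease in min. 25 points in the WOMAC Score compared to the pre-operative determined points", with a pre-operative score above 25, also at 2 years.

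On follow-up, the same row says "Patients having received the Hyperion hip replacement stem will be followed up" and states no stop at revision. On numbers, the Study Summary says "A total of 70 patients will be enrolled". The design is a single uncontrolled group.

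The General Statistical Method section opens with "Data collected in the study will be summarized descriptively". It adds "Summaries will routinely describe categorical data as counts and percentages" and "Routine summaries of implant survival will be described using the Kaplan-Meier method". Continuous data get means, medians and spread with 95% confidence intervals, and complications get frequencies and percentages.

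The supplied text names no analysis set, does not give the base of any percentage, and does not say how early revision, death or a missing 2-year score is handled in the two score endpoints.

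**The concern.** Both score endpoints read naturally as thresholds that each patient meets or misses, so a percentage meeting the threshold is the likely headline. A patient revised before 2 years can then be treated in three ways:

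1. no 2-year score is used, and the patient leaves the percentage;
2. the 2-year score is taken on the replacement implant;
3. the patient counts as a non-responder.

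The text leaves all three open, and the first two can never give a lower rate than the third. The study is meant to confirm the performance of the Hyperion system. A success rate that omits early failures, or credits them with another implant's result, could flatter the device if read alone. With no control group and no test, the percentage is itself the result, so its base matters. A base chosen after the data are seen would be open to criticism.

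**Working it through.** **Inputs.** From the Study Summary: N = 70 patients, thresholds of 4 and 25 points, and the 2-year time point. The plan gives no response rate, revision rate or derivation of the 70, so there is no figure of its own to reproduce. Assumed: f patients revised before 2 years, response proportion p among the unrevised, and response proportion q among the revised when scored on the replacement. Deaths and losses are left out to isolate revision, and all 70 are taken to meet the baseline score conditions.

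**Formulas.**

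- Revision as non-response: p(70 − f)/70.
- Revised patients excluded: p. The excess over the first rule is p·f/70.
- Revised patients scored on the replacement: [p(70 − f) + q·f]/70. The excess is q·f/70.

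Neither excess can be negative, so the direction is certain.

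**Per revision (f = 1).** Exclusion adds 0.70/70 = 1.0, 0.80/70 = 1.1, 0.85/70 = 1.2 or 0.90/70 = 1.3 points. Scoring the replacement adds 0, 0.5/70 = 0.7 or 1/70 = 1.4 points for q = 0, 0.5 or 1.

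**Whole-patient counts, response near 85%.**

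| Revised | Non-response | Excluded | Excess from exclusion | Replacement scored, at most |
|---|---|---|---|---|
| 0 | 60/70 = 85.7% | 60/70 = 85.7% | 0 | 60/70 = 85.7% |
| 3 | 57/70 = 81.4% | 57/67 = 85.1% | 3.6 | 60/70 = 85.7% |
| 5 | 55/70 = 78.6% | 55/65 = 84.6% | 6.0 | 60/70 = 85.7% |
| 7 | 54/70 = 77.1% | 54/63 = 85.7% | 8.6 | 61/70 = 87.1% |

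In the last column all revised patients meet the threshold (q = 1): 57 + 3 = 60, 55 + 5 = 60 and 54 + 7 = 61.

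**Scale.** The exact (Clopper-Pearson) 95% interval for 60/70 runs from 75.3% to 92.9%, about 18 points wide. At 3 revisions the intervals are 70.3% to 89.7% (57/70) and 74.3% to 92.6% (57/67). This shows how coarse the estimate is. It does not excuse a systematic shift, because the gap between rules is definitional and not sampling error.

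**Two limits.** If the baseline conditions reduce the denominator to n < 70, each revision among those counted moves the rate by p/n, which is more than p/70. If the thresholds are instead judged against the mean change, which the provision for continuous data allows, these percentage figures do not apply. The effect of revision on a mean cannot be sized, because the plan gives no standard deviation.

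**The case for a change.** The strongest case for a change is that two of three primary results have no stated base, that the ambiguity can only favour the device or leave it unaffected, and that repair is cheap. Revision status is already needed for implant survival, so wording and some extra tabulation would suffice. A Kaplan-Meier estimate does not correct a score percentage printed elsewhere.

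Much of this stands. The silence in the supplied text is real, the direction is certain, and the arithmetic is right. It falls short of requiring a change for four reasons.

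- **The text is partial.** What is supplied is a study summary and a short general method section. The summary points to inclusion and exclusion criteria that are not reproduced, so a rule stated in another part cannot be ruled out.
- **The responder percentage is an inference.** It is a reasonable one, but the text never says proportion of patients or success rate.
- **Too high is relative to a chosen reference.** Counting revision as non-response measures composite success. Function among patients with the implant in place, read beside implant survival, is an equally legitimate target. Imposing the first as the main summary would count one revision in all three primary endpoints.
- **Failures remain visible.** They appear in a primary endpoint at the same time point and in the complication tables. Harm requires reading a score result apart from its companion endpoint.

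**Conclusion.** No change to the plan follows. This is a gap that a competent analyst fills when reporting: give the denominator, say whether scores after revision are used, put the number revised beside each score result, and show the rate both with revision as non-response and among patients with the implant in place. Nothing stated in the plan prevents this, and no stated rule yields a wrong answer. The supplied text has no test, target rate or pass mark that the choice could tip.

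The size is 1.0 to 1.3 points per early revision under exclusion, and 0 to 1.4 points if replacement scores are used. It is zero if no implant is revised before 2 years. These figures assume that all 70 patients are counted, that 70% to 90% of unrevised patients respond, that the endpoints are reported as percentages, and that there are no deaths or losses. Gaps of 6.0 to 8.6 points need 5 to 7 early revisions in 70. The plan gives no revision rate, so it neither supports nor excludes such numbers. If that many did occur, the implant survival result would show them.

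### Does this descriptive single-arm study need a success criterion and a stated interval for 2-year implant survival?

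*Combined protocol and SAP*

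**What the plan says.** The Study Summary (Objectives/Endpoints) says that the data "will serve the purpose of confirming long-term safety and performance of the Hyperion system". The design is "Multi-center, prospective, non-controlled", the phase is post-market, and "A total of 70 patients will be enrolled". No power, target rate or expected event rate accompanies that number.

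There are three primary endpoints:

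- Merle d'Aubigné score: "increase of min. 4 points at 2 years post surgery, compared to the pre-operative score points (< 12 points").
- "Implant survival at 2 years (+/- 2 months"), with no target rate or comparator.
- WOMAC: a fall of at least 25 points at 2 years, "compared to the pre-operative determined points (WOMAC Score > 25 points pre-operative").

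Under General Statistical Method, "Data collected in the study will be summarized descriptively". Ninety-five percent limits are planned for categorical data, to assess changes over time, and for continuous data, to contrast differences. For survival the section says "Routine summaries of implant survival will be described using the Kaplan-Meier method" and nothing about an interval.

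**The concern.** A study meant to confirm something is normally expected to say what result would do so. Here no study-level success rule appears, and implant survival has no target of any kind. The planned 95% limits are tied to differences, so a literal reader could report the 2-year survival estimate with no measure of uncertainty. With 70 patients, a figure in the mid-nineties could then be presented as confirmation although survival several points lower is not ruled out.

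The score endpoints raise a related doubt. The baseline conditions (below 12 on Merle d'Aubigné, above 25 on WOMAC) suggest that the thresholds apply to each patient. The methods section names no responder proportion, however, and does not say whether patients outside those conditions are counted. If the WOMAC minimum is 0 (an assumption), a patient who starts below 25 cannot fall by 25 and is a certain non-responder if included.

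**Working it through.** **The plan's own figure.** The only number to reproduce is the enrolment of 70. It comes without alpha, power, target, expected rate or dropout, so it cannot be rederived. The counts of failures, losses and responders below are assumptions that show size only.

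**1. What the survival estimate can show.** Let S = x/n be 2-year survival with no earlier censoring. The exact interval is Clopper-Pearson. The log-log interval is S^exp(±1.96·se/(S·ln S)), with se = √(S(1−S)/n), which equals Greenwood's formula without censoring.

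For 67/70: S = 0.9571, se = √(0.9571 × 0.0429/70) = 0.0242, ln S = −0.0438. The exponent term is 1.96 × 0.0242/(0.9571 × 0.0438) = 1.13. The limits are 0.9571^exp(1.13) = 0.873 and 0.9571^exp(−1.13) = 0.986.

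| Assumed survivors | Estimate | Exact 95% | Log-log 95% |
|---|---|---|---|
| 70/70 | 100% | 94.9–100% | not estimable |
| 68/70 | 97.1% | 90.1–99.6% | 89.1–99.3% |
| 67/70 | 95.7% | 88.0–99.1% | 87.3–98.6% |
| 66/70 | 94.3% | 86.0–98.4% | 85.5–97.8% |
| 60/63 (10% loss) | 95.2% | 86.7–99.0% | 86.0–98.4% |
| 53/56 (20% loss) | 94.6% | 85.1–98.9% | 84.3–98.2% |

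The loss rows hold failures at 3 and give lost patients no follow-up. They are pessimistic for precision, but not for the estimate itself, since a lost patient might have failed.

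The lower limit lies roughly 5 to 10 points below the estimate in every row. That is a reason to print an interval. It does not make the Kaplan-Meier estimate wrong, and nothing in the methods section prevents the interval from being printed.

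**2. Does the choice of interval matter?** In the rows with failures, the two lower limits differ by about 1 point or less. That gap decides a conclusion only if there is a goal to cross. Against an illustrative 90% goal, 68/70 passes by the exact limit (90.1%) and fails by log-log (89.1%). The plan sets no goal, so no conclusion in it turns on this choice.

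**3. The responder denominator.** Take 45 responders among 70 patients, with 0, 7 or 14 patients outside the baseline conditions left out (Clopper-Pearson intervals):

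- 45/70 = 64.3% (51.9–75.4%)
- 45/63 = 71.4% (58.7–82.1%)
- 45/56 = 80.4% (67.6–89.8%)

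The spread of 80.4 − 64.3 = 16.1 points keeps the numerator at 45, so every excluded patient must be a non-responder. If the 14 excluded patients responded at the overall rate, 14 × 45/70 = 9 responders would leave with them, giving (45 − 9)/56 = 36/56 = 64.3%, which is no shift. The certain non-response argument covers WOMAC only. Nothing in the documents says that a patient at 12 or more on Merle d'Aubigné cannot gain 4 points. If the two conditions are eligibility criteria, no enrolled patient falls outside them. The Study Summary refers to inclusion and exclusion criteria, but the supplied text does not contain them.

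**4. Purpose and analysis side by side.** The Objectives sentence describes what the data are for. The methods section describes how they are summarised. Neither states a hypothesis, and neither says that the survival figure alone will be offered as confirmation. Two of the three primary endpoints do carry point thresholds, so only a study-level rule and a survival target are absent.

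**The case for a change.** The strongest case for a change is that the remedy is cheap. A named 95% interval, a stated denominator and an estimation aim need a few sentences and no new patients. Survival is a primary endpoint, few failures are likely over 2 years, and that is where a careless default misbehaves. Plain Greenwood limits at n = 70 reach 101.4%, 101.0% and 100.5% at 1, 2 and 3 failures, and have zero width at none. Fixing the method beforehand would also remove any suspicion that it was picked after the data were seen.

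Part of this stands. The interval should appear in the report, and an upper limit above 100% would be poor practice. But the plan does not propose plain Greenwood, already uses 95% limits elsewhere, and has no pass mark that a favourable method could help to reach. What remains is reporting detail that a competent analyst supplies. Adding a numerical goal is not a free improvement either. With 70 patients and an assumed true survival of 95%, an exact test against an illustrative 90% goal needs 68/70 and has power 0.31. Against 85% it needs 66/70 and has power 0.73.

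**Conclusion.** No change is called for. It is true that the supplied text has no study-level success rule, no survival target and no interval in the Kaplan-Meier sentence. These are gaps in detail in a coherent descriptive, post-market follow-up. The planned analysis still yields valid estimates, standard practice supplies the interval and the denominator, and describing the aim as estimation would leave every result as it is.

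In size, a reader who saw only 95.7% at an assumed 67/70 would miss a lower limit of about 87–88%. The denominator effect reaches 16.1 points in an extreme case and may be zero. These figures rest on assumed counts, no censoring before 2 years except where loss is stated, and a WOMAC minimum of 0. The conclusion would differ if the sponsor used the survival estimate for a formal claim against a threshold, which the documents do not say.

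### Routine complication summaries take no account of censoring; a crude percentage read as a 5-year risk would be modestly low, and adding a cumulative incidence is a cheap improvement.

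*Combined protocol and SAP*

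**What the plan says.** The Study Summary (Objectives/Endpoints) states that the data "will serve the purpose of confirming long-term safety and performance of the Hyperion system", and that to this end "the Hyperion system will be evaluated using standard scoring systems, radiographs and the reporting of adverse events". Under Safety Assessments, "Safety will be assessed by appropriate recording and reporting of adverse events throughout the study"; the study length is 12 years. Clinical visits run to 5 years. At 7 and 10 years "the patients will be asked to fill in a questionnaire recording the patients mid-to long-term clinical satisfaction".

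The General Statistical Method says "Descriptive summaries will be used for the basis of all study reports". It then treats two outcomes that accrue over time differently:

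- For complications: "Routine summaries of complication data will be in the form of frequencies and percentages"
- For the implant, by contrast: "Routine summaries of implant survival will be described using the Kaplan-Meier method"

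For complications it names no time point, no denominator and no handling of loss or death.

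**The concern.** A frequency with a percentage describes what was observed. It becomes an estimate of risk by a given time only if every patient was followed to that time, had the event, or died event-free. Otherwise the direction of the error depends on the denominator. With all enrolled below the line, events after loss are missed and the figure is low. With only patients who had an event or completed follow-up event-free, it is high.

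The plan already uses a method that allows for censoring in an adjacent sentence, but for implant survival. Complications that end in implant failure are covered there; other complications are not. Adverse event reporting is one of three stated means of evaluating the device, so a reader of a study report is likely to take the complication percentage as a risk over the follow-up period.

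**Working it through.** The documents give no complication, loss or death rate and no target figure, so there is nothing to reproduce. What follows is illustrative.

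**Inputs.** From the documents: 70 patients, visits to 5 years, questionnaires at 7 and 10 years, 12-year study. Assumed: true 10-year risk 20%; loss hazard c of 0.01, 0.03, 0.05 or 0.08 per year, unrelated to complications; no deaths unless stated. Two shapes of complication hazard:

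- Constant: h = -ln(0.8)/10 = 0.0223 per year.
- Early: 80% of the cumulative hazard in year 1, so a = 0.1785 in year 1 and b = 0.00496 per year after.

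**Formulas for a percentage of all enrolled, with everyone's time point T reached.**

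- Constant: E = h/(h+c) × (1 - exp(-(h+c)T)); true risk 1 - exp(-hT).
- Early: E = a/(a+c) × (1 - exp(-(a+c))) + exp(-(a+c)) × b/(b+c) × (1 - exp(-(b+c)(T-1))).

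Example, constant, c = 0.05, T = 5: 0.0223/0.0723 × (1 - exp(-0.3616)) = 0.3086 × 0.3034 = 0.0936, against 1 - exp(-0.1116) = 0.1056.

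**Results at 5 years.**

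| Loss per year | Constant (true 10.6%) | Shortfall, points | Early (true 18.0%) | Shortfall, points |
|---|---|---|---|---|
| 1% | 10.3% | 0.3 | 17.9% | 0.1 |
| 3% | 9.8% | 0.7 | 17.6% | 0.4 |
| 5% | 9.4% | 1.2 | 17.4% | 0.6 |
| 8% | 8.7% | 1.8 | 17.0% | 1.0 |

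The largest shortfall, 1.8 points, is 0.018 × 70 = 1.3 patients. At 2 years, even with 8% loss, the figures are 4.0% against 4.4% (constant) and 16.1% against 16.8% (early).

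**Staggered entry, no loss.** Twelve years less ten of follow-up suggests about 2 years of accrual; this is inferred, not stated. In a report 5 calendar years after first entry, follow-up is then uniform over 3 to 5 years. Constant: 1 - (exp(-3h) - exp(-5h))/(2h) = 8.5%, against 10.6%. Early: 17.6% against 18.0%. If the report waits until all reach 5 years, this error disappears.

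**Results at 10 years.** All enrolled, against 20%, for 1%, 3%, 5% and 8% loss: 19.1%, 17.4%, 15.9%, 14.0% (constant); 19.7%, 19.2%, 18.8%, 18.1% (early).

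**Effect of death.** With death hazard d as a competing event, the target becomes h/(h+d) × (1 - exp(-(h+d)T)), and c + d replaces c in E. If half of 5% annual attrition is death (c = d = 0.025), the 10-year constant-hazard target is 17.8% and E is 15.9%, 1.9 points low; with the early hazard it is 0.6 points low. If all attrition is death, c = 0, E equals the target, and there is no error.

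**Other denominator.** Events divided by events plus event-free completers is E/(E + C), where C is the probability of being event-free and still followed at T. At 5% loss and no deaths this gives 11.8% (constant) and 21.4% (early) at 5 years, and 24.7% and 27.9% at 10 years.

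**Sampling error.** In simulation (n = 70, 3,000 runs per scenario), the 95% interval for the Aalen-Johansen estimate at 5 years averaged 14.2 to 15.5 points wide (constant) and 17.6 to 18.0 (early). At 10 years it averaged about 18 to 22 points.

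**The case against.** Three points stand.

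1. The plan speaks of routine summaries and does not exclude others. A reader might infer that complications will be reported only as crude percentages, but the text does not say so. It can be said only that no censoring-aware summary appears in it. The text is also headed as a study summary and refers to eligibility criteria that it does not list, so it may not be the whole plan.
2. The plan never calls the percentage a 5- or 10-year risk. That reading is inferred from the long-term purpose, the study length and the recording of adverse events throughout. The general statement on categorical data, with 95% limits for differences over time, leaves room for tables by time point.
3. At 5 years the error is about one patient or fewer and well inside sampling error. Complications are not a primary endpoint, and implant survival, which is one, already has Kaplan-Meier.

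A reader might also infer from the 10-year or completer-denominator figures that long-term risk would be badly misstated. The documents do not support that: they name neither that denominator nor a 10-year complication percentage, and the large values need heavy loss that is not death.

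What the objection does not remove is that the error is systematic when there is loss, and that the plan does not state which denominator a reader should assume.

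**Conclusion.** The point holds as a low-severity improvement to reporting, not as an error in the plan. Under the assumed 20% 10-year risk, with no deaths and 1% to 8% annual loss, an all-enrolled percentage read as a 5-year risk is 0.3 to 1.8 points low with a constant hazard and 0.1 to 1.0 with an early one. A report issued before all patients reach 5 years can add an error of similar size. The 10-year error could reach about 4 points at 5% loss (15.9% against 20%, constant hazard), less if part of the attrition is death. With 70 patients the bias is usually smaller than sampling error. All sizes assume that loss is unrelated to complications.

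**What to change.** Keep the frequency table, with patients having at least one event as the unit and the denominator printed. Add the Aalen-Johansen cumulative incidence of first complication, with death as a competing event and censoring at last contact, for any complication. Report it at 2 and 5 years with the 95% confidence interval and number at risk. One minus Kaplan-Meier is not a substitute, because it overstates risk when patients die event-free. Categories too sparse for this keep the count, denominator and exact 95% limits; for example, 0 of 70 has an upper limit of 1 - 0.025^(1/70) = 5.1%. Any 10-year value should carry a statement on how completely complications were ascertained after year 5, since the only later contacts named are the two questionnaires.

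The cost is SAP wording and a little programming, with no change to sample size or visits. Onset, death and last-contact dates are needed. Kaplan-Meier for implant survival already needs the last of these; the text does not confirm that the others are captured. The intervals will be wide, and pooling all complications mixes unlike events. The method does not cure under-ascertainment or loss related to complications.
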